### 7.2.1 Determination of Reporting Requirements

Reporting requirements may include the following considerations: 1) whether the patient has received an investigational or commercial agent; 2) the characteristics of the adverse event including the grade (severity), the relationship to the study therapy (attribution), and the prior experience (expectedness) of the adverse event; 3) the Phase (1, 2, or 3) of the trial; and 4) whether or not hospitalization or prolongation of hospitalization was associated with the event.

### 7.2.2 Steps to determine if an adverse event is to be reported in an expedited manner:

Step 1: *Identify the type of event using the NCI Common Toxicity Criteria (CTC).*

The CTC provides descriptive terminology and a grading scale for each adverse event listed. A copy of the CTC can be downloaded from the CTEP home page (<http://ctep.cancer.gov>). Additionally, if assistance is needed, the NCI has an Index to the CTC that provides help for classifying and locating terms. All appropriate treatment locations should have access to a copy of the CTC.

Step 2: *Grade the event using the NCI CTC.*

Step 3: *Determine whether the adverse event is associated to the protocol therapy (investigational or commercial).*

Attribution categories are as follows: Unrelated, Unlikely, Possible, Probable, and Definite.

Step 4: *Determine the prior experience of the adverse event.*

Step 5: *Review 10.2 to determine if there are any protocol-specific requirements for reporting of specific adverse events that require special monitoring.*

Step 6: *Determine if the protocol treatment given prior to the adverse event included investigational agent(s), a commercial agent(s), or a combination of investigational and commercial agents.*

### **7.3 Reporting Methods**

7.3.1 All serious, unusual life-threatening or lethal adverse which may be study related will be reported within 24 hours by telephone to the Principal Investigator and must be followed by a written report which must be received by the Principal Investigator within 10 business days. The Principal Investigator shall also be responsible for promptly notifying the local Institutional Review Board of all such serious adverse events. For all fatal events (Grade 5) while on study or within 30 days of treatment, a written report will follow within 10 working days.

7.3.2 IRB Reporting

7.3.2.1 All unexpected adverse events, serious adverse events, events that are more severe than anticipated, events that are more frequent than anticipated, and deaths must be reported to the IRB within ten (10) working days of being made known to the Principal Investigator.

## **8.0 CRITERIA FOR DISCONTINUATION OF A PATIENT FROM THE STUDY**

**8.1.1.** Disease progression

**8.1.2.** Unacceptable surgical adverse event that preclude administration of radiation treatment.

**8.1.3.** Patient decides to withdraw from the study

**8.1.4.** At any time, the patient or his/her physician may discontinue participation in the study if this is believed to be in the patient's best interest.

## 9.0 DATA REPORTING

Basic forms include

- On-study information, including patient eligibility data and patient history
- Flow-sheets, tumor/disease assessment forms or other forms for interim monitoring
- Specialty forms for pathology, radiation or surgery
- Off-study summary sheet, including a final assessment by the treating physician
- Follow-up forms when required.

The following can be used for the location if using SCCC forms.

Data must be submitted according to the protocol requirements for ALL patients registered. Patients for whom documentation is inadequate to determine eligibility will generally be deemed ineligible.

A list of forms to be submitted, as well as expectation dates, is found in Appendix IV.

## 10.0 STATISTICAL CONSIDERATIONS

### 10.1 Study Size

For the purpose of dose escalation of NAC-radiation treatment, **evaluable patients** will be defined as any eligible patient that begins NAC irradiation treatment. However to evaluate feasibility of the NAC-sparing mastectomy with reconstruction, any patient who undergo surgery will be considered evaluable.

Following the dose escalation/de-escalation procedure described in section 4.2, we anticipate that 12 to 18 evaluable patients will be enrolled in this phase I study *during the dose-finding part*. The **number of evaluable patients** that will be needed depends on the number of times the NAC-radiation dose is escalated or possibly de-escalated. If the escalation occurs from dose level II up to dose level IV, between 14-18 evaluable patients will be required. If the dose is de-escalated after dose level II been evaluated in 6 patients, then 12 evaluable patients will be required, assuming 6 patients would be evaluated at dose level I. With 6 evaluable patients, the probability of not escalating when the true DLT rate is 35% is 68%. If the true DLT rate is 20%, the probability that the dose will be escalated is 66%.

A maximum of 6 patients per year is expected to be enrolled, since each patient must be evaluated for a minimum of 35 days and at most two patients will be enrolled simultaneously (within < 30 days after completion of the 5 days NAC radiation treatment). Thus, the expected accrual period is between 2-3 years.

An **additional expansion cohort of 12 patients** will be enrolled at the “**potential**” **recommended phase II dose (RP2D)** over an expected accrual period of 2 years.

To gather data on recurrence and survival, all patients will be followed at their clinic visits as clinically indicated.

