## 5.9 RESPONSE CRITERIA

- 5.9.1** The definition of local recurrence is histologic evidence of recurrent carcinoma, either invasive or non-invasive in the nipple-areola complex in the ipsilateral breast.
- 5.9.2** Clinical evidence of carcinoma by physical exam and/or mammograms/MRI will not be evidence of local recurrence until biopsy proof.
- 5.9.3** **Overall survival time** is defined from the date of surgery until the date of death due to any cause. In the absence of death, follow-up time will be censored by the date of last contact.
- 5.9.4** **Disease-free survival time** is defined from the date of surgery until the date of documented recurrence (local or distant) or breast cancer-related death, whichever occurs first. Patients who die without documentation of recurrence will be considered to have had disease recurrence at the time of death, unless there is documented evidence that no recurrence occurred before death. In other words, 'unknown cause of death' will be considered an event for the disease-free survival analysis. In the absence of any event defining disease recurrence, follow-up time will be censored at the date of last documented recurrence-free status.

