## 10.2 Planned Analysis

**Patient demographics** (age, race/ethnicity), **laboratory parameters, disease characteristics** (such as, tumor stage, grade), will be summarized using descriptive statistics: counts and percentages, range, median, mean, and standard deviation, as appropriate [23].

**Toxicities** resulting from radiation treatment will be tabulated by type, grade, duration, and attribution to treatment according to NCI CTCAE version 3.0, and by administered NAC radiation dose. A patient-level summary by worst grade toxicity will be included. Any grade 3, 4 or 5 or unexpected lower grade toxicities will be reported.

**Intraoperative parameters and perioperative parameters** (complications, events, and findings) will be described in the operative report as routinely done.

**Surgery success rate**, defined as the proportion of patients who had successful NAC sparing surgery with reconstruction divided by the total number of study patients, will be determined.

**Cosmetic results** will be assessed by both the physician(s) and the patients at 3, 6 and 12 months, using a 4-category ordinal scale (excellent, good, fair, and poor). Data will be summarized in terms of number and % of patients in these 4 possible categories at those assessment times separately for assessment by physician and by patient. Statistical analysis methods for contingency tables will be used to compare changes over time for each evaluator (physician or patient), and also to compare agreement between physician and patient assessment at a given time. [24]

To gather data on recurrence and survival, all patients will be under follow-up for a minimum of 5 years, unless they withdraw consent or die within that time.

Given the small study size and the expected low incidence of recurrence, we do not expect any such recurrences within 5 years. However, if patients do recur, the **number of recurrences** will be reported, along with corresponding summary regarding time to recurrence, type of recurrence -- local (ipsilateral nipple-areola recurrence in-field, peripheral, or extra-field location) or distant, irradiated volume, and radiation dose. If the number of events allows, **disease-free survival and overall survival** will be estimated by the Kaplan-Meier method. [25]

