## APPENDIX I (02-21-2013)

STUDY PARAMETER TABLE (See Section 5.0 for details)										
	SURGERY			PRIOR to RT	DURING RT	FOLLOW-UP AFTER TREATMENT			Long-term Follow-up	
Assessment	Pre-Op	Intra-Op	Post-Op	PRIOR to RT		From END of RT			From End of RT	
		Week 1-4		Week 1-7	Week 5-8	1 Mo ± 1 wk.	3 Mo ± 2 wks	6 Mo ± 2 wks	12 Mo ± 2 wks	Thereafter, Every 6 Mo (± 1 Mo) and in years 2-5 at the discretion of the Investigator
Informed Consent	X									
Biopsy	X									
Surgical Frozen Section Path		X								
Pathology	X		X							
History/Physical	X		X	X	X	X	X	X	X	
ECOG 0-2	X			X		X	X	X	X	
Mammogram	X									
Pregnancy test	X									
Labs per MD discretion	X									
Radiological tests per MD discretion	X	X								
Operative Report			X							
Photographs *				X		X	X	X	X	
NAC sparing mastectomy		X								
RT Treatment Plan					X					
Cosmesis				X		X	X	X	X	
AE Evaluation			X	X	X	X				

\* Photographs will be taken at the discretion of the PI and Sub-PI

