**Appendix IV:****DATA SUBMISSION SCHEDULE**

FORM	TO BE COMPLETED
BASELINE	
Eligibility Checklist	
SCCC Protocol Enrollment Form	Prior to registration
Consent Forms Signed/dated	
On-study Form	Within 30 days of registration
DURING PROTOCOL THERAPY	
	Due every week for phase I studies, every cycle for phase II-IV studies
AFTER PROTOCOL THERAPY	
Off Treatment Form	Within 14 days of discontinuation/completion of protocol therapy
FOLLOW-UP SCHEDULE (for studies with long term follow-up)	
Follow-up Form	1 month, 3 month, 6 month, 1 year, then every 6 months (+/- 1 month) and in years 2-5, at the discretion of the Investigator.
Progression/Relapse	Within 4 weeks of knowledge of progression/relapse
Notice of Death Form	Within 4 weeks of knowledge of death
Subsequent Malignancy	Within 4 weeks of knowledge of another malignancy

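### The 5-year minimum follow-up in section 10.2 has no schedule to deliver it: Appendices I and IV leave years 2-5 to discretion, so a count of zero recurrences could not be interpreted

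*Combined protocol and SAP*

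**What the plan says.** Section 2.2 makes survival and recurrence part of the secondary objectives. How long and how often patients are followed for them is set in several places:

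- Section 10.2: "all patients will be under follow-up for a minimum of 5 years, unless they withdraw consent or die within that time".
- Section 10.1, for the same purpose: "all patients will be followed at their clinic visits as clinically indicated". It gives no duration or interval.
- Appendix I, long-term follow-up column after month 12: "Thereafter, Every 6 Mo (± 1 Mo) and in years 2-5 at the discretion of the Investigator".
- Appendix IV, follow-up form, after the 1-, 3-, 6-month and 1-year forms: "then every 6 months (+/- 1 month) and in years 2-5, at the discretion of the Investigator".
- Section 5.8 lists vital status, disease status, and site and date of first failure as follow-up data, without timing.

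Section 5.9.4 says that for a patient without a disease-free survival (DFS) event "follow-up time will be censored at the date of last documented recurrence-free status". For overall survival, under 5.9.3, "follow-up time will be censored by the date of last contact". Both times start at surgery. Appendix IV also requires a progression/relapse form "Within 4 weeks of knowledge of progression/relapse", with the same limit for deaths.

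Section 10.2 expects no recurrences within 5 years, will report the number if any occur, and will use Kaplan-Meier only if there are enough events. Section 8.1.1 lists disease progression as a reason to discontinue a patient from the study.

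**The concern.** The analysis section makes a commitment that the operational schedule does not require anyone to keep. Sites work from the visit table and the form schedule. After month 12 these name a six-monthly interval and, in the same phrase, make years 2-5 discretionary, so it is unclear whether any assessment is mandatory from year 2 on. Neither 10.1 nor 5.8 supplies an interval that would fill the gap.

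At stake is what the recurrence result will mean. If the report says that no recurrences were seen, the reader must know how many patients were actually established to be recurrence-free, and for how long. The plan does not ask for that number. In addition, the DFS censoring date is the last documented recurrence-free date, so discretionary visits set the censoring times directly.

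**Working it through.** No sample size, power figure or recurrence rate in the plan depends on follow-up, so there is no stated figure to reproduce. The check compares the passages and then uses labelled assumptions to show size and direction.

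**1. Comparison.** Sections 10.1 and 10.2 can be read together, one giving the occasion of visits and the other the duration. Section 10.2 and the appendices are harder to reconcile: a minimum for all patients, excused only by death or withdrawn consent, against assessments in years 2-5 that the investigator may omit. Section 8.1.1 adds a second tension, because 10.2 does not list progression as an exception.

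**2. Value of a zero count.** Planned patients: 12 to 18 in dose finding plus 12 in expansion, so 24 to 30. With 0 events in n patients, the exact one-sided 95% upper bound is 1 − 0.05^(1/n).

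| Patients with known status | Upper bound |
|---|---|
| 30 (all) | 9.5% |
| 15 (assumed half) | 18.1% |
| 24 (all) | 11.7% |
| 12 (assumed half) | 22.1% |

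**3. How much of the risk lies in the discretionary period.** Assume a constant hazard and 5-year risk R. The 1-year risk is 1 − (1 − R)^(1/5). For R = 10% (assumed) it is 1 − 0.9^0.2 = 2.09%, so 1 − 2.09/10 = 79% of 5-year recurrences fall after month 12. The share is about 80% for R = 2% or 5%.

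**4. Events that could be missed.** The documents give no recurrence rate, so R is assumed. Expected events are nR. If 75% are captured (assumed), the loss is 0.25nR:

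| R | Expected, n = 24 to 30 | Lost at 75% capture |
|---|---|---|
| 2% | 0.5 to 0.6 | 0.1 to 0.15 |
| 5% | 1.2 to 1.5 | 0.3 to 0.4 |
| 10% | 2.4 to 3.0 | 0.6 to 0.75 |

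As a worst case, take n = 30 and R = 10%, and suppose that no recurrence in an unassessed patient ever becomes known. If half the patients are unassessed after month 12, 30 × (0.5 × 0.10 + 0.5 × 0.0209) = 1.81 of 3.0 events are captured. If all are unassessed, 30 × 0.0209 = 0.63 are captured.

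**5. Direction of bias.** Large-sample simulation with true 5-year risk 10%, constant hazard, and 25% of patients leaving follow-up between years 1 and 5 (all assumed):

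| Who is lost | Crude proportion | Kaplan-Meier |
|---|---|---|
| (a) Loss unrelated to recurrence | 9.1% | 10.0% |
| (b) Symptoms bring patients in, so those who recur are seen | 10.0% | 11.1% |
| (c) Patients who recur after year 1 are lost twice as often, before the recurrence | 6.1% | 6.8% |

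Kaplan-Meier is unbiased in (a), too high in (b) and too low in (c). The crude count is low in (a) and (c) but not in (b).

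**The case against.** The strongest reply is that discretionary visits are not absent visits. The status items are already listed in 5.8 with no 12-month limit. Relapse and death forms are due on knowledge of the event, whatever the visit schedule. The endpoint is descriptive, the plan promises Kaplan-Meier only if events allow and names no 5-year estimate, and no dose decision, stopping rule or sample size rests on it. At an assumed risk of 2% to 5% with 75% capture, the expected loss is under half an event.

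Most of this stands, and it limits the size of the point. It does not remove it. A form triggered by knowledge of a relapse records known events; it cannot show that a patient nobody has seen is recurrence-free, and that is what a zero count and the DFS censoring date both need. Listing the items without timing does not secure the 5-year minimum either.

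A reader might go further and infer that recurrences will be under-counted and that censoring will be informative. The documents support neither as a certainty. In particular, visits prompted by symptoms would tend to capture recurrences and push Kaplan-Meier upward, as in (b), rather than cause an under-count. A reader might also take the long-term column of Appendix I, in which no assessment appears to be marked, as proof that nothing is collected. That may be an effect of how the table was extracted, and nothing here relies on it.

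**Conclusion.** The mismatch is real and should be corrected. Section 10.2 states a 5-year minimum for all patients, and no schedule in the plan makes it happen in years 2-5. Under-ascertainment and informative censoring are possible, with a direction that cannot be known in advance.

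The size is modest for the trial as a whole: a secondary, descriptive endpoint in about 24 to 30 patients, with the primary objective untouched. The main loss is that the expected result, no recurrences, could not be interpreted without a known denominator; the upper bound moves from 9.5% to 18.1% if 15 rather than 30 patients are ascertained. The 15, the recurrence rates, the capture rates and the loss patterns are assumptions. The worst-case capture figures (1.81 or 0.63 of 3.0) are illustrations, not forecasts, because they ignore relapses that become known without a scheduled visit.

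**What to change.** - Reconcile section 10.1 and Appendices I and IV with the 5-year minimum in 10.2, and remove the ambiguity between six-monthly and discretionary follow-up from year 2.
- Require vital status and disease status (date and site of first failure) to be recorded at least yearly to year 5, by record review or telephone if there is no visit. Apply this to all patients in the DFS and overall survival analyses. Because both times start at surgery, state whether patients operated on but never irradiated are included.
- Leave visits and tests for care at the investigator's discretion.
- Reconcile 8.1.1 with 10.2, so that it is clear how survival follow-up continues after progression.
- Report median follow-up and the number of patients with complete 5-year status beside the recurrence count.

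The cost is amended wording in these sections and about one status contact per patient per year for roughly 24 to 30 patients, plus any operated on but not irradiated if they are included. No procedure is added, and no patients need to be added to the trial.

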## 10.2 Planned Analysis

**Patient demographics** (age, race/ethnicity), **laboratory parameters, disease characteristics** (such as, tumor stage, grade), will be summarized using descriptive statistics: counts and percentages, range, median, mean, and standard deviation, as appropriate [23].

**Toxicities** resulting from radiation treatment will be tabulated by type, grade, duration, and attribution to treatment according to NCI CTCAE version 3.0, and by administered NAC radiation dose. A patient-level summary by worst grade toxicity will be included. Any grade 3, 4 or 5 or unexpected lower grade toxicities will be reported.

**Intraoperative parameters and perioperative parameters** (complications, events, and findings) will be described in the operative report as routinely done.

**Surgery success rate**, defined as the proportion of patients who had successful NAC sparing surgery with reconstruction divided by the total number of study patients, will be determined.

**Cosmetic results** will be assessed by both the physician(s) and the patients at 3, 6 and 12 months, using a 4-category ordinal scale (excellent, good, fair, and poor). Data will be summarized in terms of number and % of patients in these 4 possible categories at those assessment times separately for assessment by physician and by patient. Statistical analysis methods for contingency tables will be used to compare changes over time for each evaluator (physician or patient), and also to compare agreement between physician and patient assessment at a given time. [24]

To gather data on recurrence and survival, all patients will be under follow-up for a minimum of 5 years, unless they withdraw consent or die within that time.

Given the small study size and the expected low incidence of recurrence, we do not expect any such recurrences within 5 years. However, if patients do recur, the **number of recurrences** will be reported, along with corresponding summary regarding time to recurrence, type of recurrence -- local (ipsilateral nipple-areola recurrence in-field, peripheral, or extra-field location) or distant, irradiated volume, and radiation dose. If the number of events allows, **disease-free survival and overall survival** will be estimated by the Kaplan-Meier method. [25]

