**(See section 4.2 for further details.)**

## **HYPOTHESIS:**

- The use of NAC-sparing mastectomy followed by postoperative NAC (nipple-areola complex) external beam radiotherapy for selected patient with early stage invasive or in-situ breast cancers will be technically feasible and with acceptable complication rates.
- The cosmetic results after NAC-sparing mastectomy followed by postoperative external beam radiotherapy to the NAC will be better comparable with Skin Sparing Mastectomy.
- The local control rate in the NAC will be more than expected for a NAC sparing mastectomy without postoperative radiotherapy.
- The patient's satisfaction after NAC-sparing mastectomy followed by postoperative NAC external beam radiotherapy will be better than after Skin Sparing Mastectomy.

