#### **4.2.6 Definition of dose limiting toxicity (DLT)**

Dose limiting toxicity (DLT) is defined as any of the following toxicities occurring during radiation treatment period plus an **additional observation period of 30 days** following completion of NAC radiation:

- a) Grade 4 skin rash
- b) Grade 4 pain
- c) NAC necrosis
- d) Any toxicity requiring interruption of the NAC irradiation by > 2 weeks (14 calendar days), except if interruption is secondary to LINAC machine or unpredictable weather problems or unrelated medical conditions that would prevent the subject to come for treatment.
- e) Any grade 4 or 5 treatment-related toxicity

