### 7.1 Definitions:

7.1.1 **Adverse events** (AE's) will use the descriptions and grading scales found in the NCI Common Toxicity Criteria in Appendix II.

**Adverse events:** Any unfavorable and unintended sign (including abnormal laboratory finding), symptom, or disease temporally associated with the use of a medical treatment or procedure, regardless of whether it is considered related to the treatment or procedures; also and “unanticipated problem” of any nature (e.g., psychological or social harm)

7.1.2 A **serious adverse event** (experience) or reaction is any untoward medical occurrence that at any dose: results in death, is life-threatening, requires inpatient hospitalization or prolongation of existing hospitalization, results in persistent or significant disability/incapacity, or is a congenital anomaly/birth defect.

The definition of serious adverse event (experience) also includes **important medical events**. Medical and scientific judgment should be exercised in deciding whether reporting is appropriate in other situations, such as important medical events that may not be immediately life-threatening or result in death or hospitalization but may jeopardize the patient or **may require intervention** to prevent one of the other outcomes listed in the definition above. These should also usually be considered serious. Examples of such events are intensive treatment in an emergency room or at home for allergic bronchospasm; blood dyscrasias or convulsions that do not result in hospitalization; or development of drug dependency or drug abuse.

7.1.3 **Expected events** are those that have been previously identified as resulting from administration of the treatment.

7.1.4 An adverse event is considered **unexpected** when either the type of event or the severity of the event is *not* listed in: the current NCI Agent-Specific Adverse Event List; the investigator's brochure or the information section of this protocol.

7.1.5 The definition of **related** is that there is a reasonable possibility that the drug caused the adverse experience.

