## **10.3 Interim Monitoring**

### **10.3.1 Role of the Research Team and the DSMC**

The Research Team will continuously monitor study accruals and adverse events from both surgery and radiation treatment. In particular, for the purpose of escalation and de-escalation (section 4.2) patients will be monitored closely during the 30 days after completion of NAC radiation treatment, and subsequently for any toxicity or adverse reaction to treatment. All toxicities, regardless their grade, will be recorded in the patient case report form using NCI/CTEP Common Terminology Criteria for Adverse Events (CTCAE) version 3.0.

The Sylvester Comprehensive Cancer Center's Data and Safety Monitoring Committee (DSMC) will monitor this protocol according to the Cancer Center's DSM Plan. In its oversight capacity, the DSMC bears responsibility for suspending or terminating this study.

DSMC oversight of the conduct of this trial includes ongoing review of accrual and adverse event data. The guidelines appearing in Sections 10.3.2, and 10.3.3 are offered for DSMC consideration in assessing accrual, adverse events. In addition, the DSMC will review reports from all audits, site visits, or study reviews pertaining to this clinical trial and take appropriate action.

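### Section 10.2 limits the by-dose toxicity table to radiation effects, but DLT items a to c set no condition on cause, so a nipple-areola necrosis judged surgical can count as a DLT and be missing from that dose's table

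*Combined protocol and SAP*

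**What the plan says.** **The planned table.** Section 10.2 (Toxicities) covers toxicities "resulting from radiation treatment will be tabulated by type, grade, duration, and attribution to treatment according to NCI CTCAE version 3.0". The same table is split by the radiation dose given. The section adds a per-patient summary by worst grade and one further sentence: "Any grade 3, 4 or 5 or unexpected lower grade toxicities will be reported". That sentence has no limit on cause and no breakdown by dose.

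**The DLT list.** Section 4.2.6 gives five items, counted from the start of irradiation to 30 days after its end. Item "c) NAC necrosis" stands without a grade and without a cause. Items a (grade 4 skin rash) and b (grade 4 pain) also name no cause. Item d excludes treatment breaks due to machine faults, weather or unrelated medical conditions. Item e is limited to treatment-related events. Under Section 4.2.5, two DLT patients among 2 to 6 make a dose unacceptable.

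**Data capture.** Section 7.1.1 defines an adverse event "regardless of whether it is considered related to the treatment or procedures", and Section 10.3.1 states: "All toxicities, regardless their grade, will be recorded in the patient case report form". Section 5.8.9 collects events from the post-operative visit to 30 days after radiation. Section 7.2 leaves out chemotherapy-related events from 2 weeks after radiation.

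**The cause of NAC necrosis.** It is named as a risk of the surgery (6.1.2), as a risk of the added irradiation (6.2.1 and 6.3.1), and as an unacceptable surgery-related toxicity (10.3.3).

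**The concern.** The count that decides on a dose level and the table that describes it are defined over different sets of events. NAC necrosis is where they are most likely to part: it is a DLT at any grade, the protocol attributes it to both modalities, and in a single-arm, open trial its cause is the treating team's judgement.

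If a necrosis is put down to surgery, the reader of the final report may see a dose level closed for toxicity beside a table that does not show the event. The first hypothesis, that the combined procedure is "technically feasible and with acceptable complication rates", concerns surgery followed by radiotherapy. A table filtered to one cause cannot describe that complication rate.

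**Working it through.** **1. The plan's own figures.** Section 10.1 gives two operating characteristics for six patients, with two DLTs as the stopping count. With X binomial(6, p), a level closes when X ≥ 2.
- p = 0.35: 1 − 0.65⁶ − 6(0.35)(0.65⁵) = 0.681 (stated 68%).
- p = 0.20: 0.80⁶ + 6(0.20)(0.80⁵) = 0.655 (stated 66%).

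Both reproduce. The point contests neither.

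**2. The DLT items against the table.**

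| Item in 4.2.6 | Condition on cause | In a radiation-only table? |
|---|---|---|
| a, b: grade 4 rash, grade 4 pain | None | Only if judged a radiation effect |
| c: NAC necrosis | None, and no grade threshold | Only if judged a radiation effect |
| d: treatment break over 14 days | Machine, weather and unrelated conditions excluded | Cause already restricted |
| e: other grade 4 or 5 | Treatment-related only | Yes, if treatment means the irradiation |

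The mismatch is therefore in items a to c.

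**3. What the unfiltered sentence in 10.2 catches.** Grade 4 rash and pain are caught whatever their cause, though not by dose. A necrosis of grade 3 or more is caught in the same way. A necrosis below grade 3 is caught only if unexpected. It is a listed risk in Section 6, so it would ordinarily be expected under 7.1.3 and 7.1.4. No section plans a table of DLTs by dose level.

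**4. Size per event.** Section 4.2.7 pools 6 + 12 = 18 patients at the recommended dose. One omitted necrosis lowers the tabulated rate by 1/18 = 5.6 percentage points. In the extreme case of a six-patient level closed by two necroses both judged surgical, the DLT count is 2/6 = 33% and the table shows 0/6.

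**5. How often (illustration only).** The documents give no rate q of surgically attributed necrosis within the DLT window, so q = 2%, 5% and 10% are assumptions. So are a radiation DLT rate r = 10% and independent causes. The total rate is t = 1 − (1 − q)(1 − r).

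| q | t | P(two or more surgical necroses in 6) | P(level closes), rate t | P(level closes), rate r alone | Difference |
|---|---|---|---|---|---|
| 2% | 11.8% | 0.6% | 15.1% | 11.4% | 3.7% |
| 5% | 14.5% | 3.3% | 21.2% | 11.4% | 9.8% |
| 10% | 19.0% | 11.4% | 32.0% | 11.4% | 20.6% |

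The last column is the chance that a level closes while a radiation-only table shows fewer than two DLT patients, as if all six were always treated. If the level stops at its second DLT patient, the chance is P(level closes) × [1 − (r/t)²]: 0.1513 × 0.282 = 4.3%, 0.2118 × 0.524 = 11.1% and 0.3201 × 0.723 = 23.1%.

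**The case against.** **The exclusion is not certain.** The same sentence classifies events by attribution, and Section 7.2.2 runs the categories from Unrelated to Definite. That classification has little purpose if unrelated events have already been removed. Section 10.3.2 also treats the 4.2.5 rules as the stopping rules for radiation-related toxicity, which suggests that items a to c may be meant as radiation effects. Both points stand as possible readings. But on the first, the opening limitation in 10.2 is contradicted by its own classification. On the second, 4.2.6 does not say what is meant. Either way the wording has to be reconciled.

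**Ambiguous events would mostly stay in.** Section 10.3.2 counts possible attribution as radiation-related, and a necrosis arising after irradiation begins would often be rated at least possible. This stands: the loss needs a judgement of Unlikely or Unrelated.

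**Surgical necrosis is watched elsewhere.** Section 10.3.3 gives it a stopping guideline. That guideline is not by radiation dose, so it does not fill the gap.

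**Stronger readings that the documents do not support.** A reader might infer any of the following:
- That item d also counts events of any cause. It excludes unrelated medical conditions.
- That a single necrosis closes a level. Two DLT patients are needed.
- That the table determines the recommended dose. Escalation and the maximum tolerated dose follow from DLT counts (4.2.5), and the expansion cohort has its own guideline (10.3.2).
- That an any-cause necrosis rate applied to 18 patients gives the number of events lost. Only the share judged surgical would be lost, and no such share is given. The necrosis figures for the intra-operative electron series in Section 1.2 do not supply one, because that series combined surgery and radiation.

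**Conclusion.** The point holds as a weakness in reporting. Read literally, Section 10.2 filters the by-dose table by cause and DLT items a to c do not, so a NAC necrosis judged surgical can count toward closing a level and be missing from that level's table. The unfiltered sentence on grade 3 to 5 and unexpected events narrows the gap without closing it.

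The size per event is firm: 5.6 percentage points among 18 patients. The frequency is not. The range of about 4% to 21% (4% to 23% with stopping at the second DLT patient) for a level that closes without two DLT patients in the table rests wholly on the assumed rates and on independence. No escalation decision changes. What is affected is the safety profile reported for each dose and the ability to describe the complications of the combined procedure. The change is worth making because the data are already collected.

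**What to change.** In Section 10.2:
- Tabulate by dose level all adverse events collected under 5.8.9 in patients who begin irradiation, regardless of attribution, except the chemotherapy-related events excluded in 7.2.
- Show onset before and after the first fraction separately, so that the table can address the first hypothesis without mixing earlier surgical events into the radiation period.
- Put the possibly, probably or definitely radiation-related subset in an adjacent column.
- Add DLT counts by item and dose level, with an any-cause row for NAC necrosis, so that the table can be checked against the dose decisions.

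The attribution wording of Sections 4.2.6 and 10.2 must also be reconciled. Which events should count as DLTs is for the investigators to state.

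The cost is a few sentences in 10.2 and one extra column, with no new data collection. The downside is that any-cause rates will look slightly higher than radiation-only rates. Patients who have surgery but never start irradiation have no dose level and remain outside this table.
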